12.5 Liver Safety Monitoring and Assessment

Any subject enrolled in a clinical study with active drug therapy and reveals an increase of serum aminotransferases (AT) to $> 3 \times \text{ULN}$ or bilirubin $> 2 \times \text{ULN}$ should undergo detailed testing for liver enzymes (including at least ALT, AST, alkaline phosphatase [ALP] and TBL). Testing should be repeated within 72 hours of notification of the test results. For studies for which a central laboratory is used, alerts will be generated by the central laboratory regarding moderate and severe liver abnormality to inform the investigator and study team. Subjects should be asked if they have any symptoms suggestive of hepatobiliary dysfunction.

Definition of Liver Abnormalities

Confirmed abnormalities will be characterized as moderate and severe where ULN:

	ALT or AST		TBL
Moderate	$> 3 \times \text{ULN}$	or	$> 2 \times \text{ULN}$
Severe	$> 3 \times \text{ULN}$	and	$> 2 \times \text{ULN}$

In addition, the subject should be considered to have severe hepatic abnormalities for any of the following:

- ALT or AST $> 8 \times \text{ULN}$.
- ALT or AST $> 5 \times \text{ULN}$ for more than 2 weeks.
- ALT or AST $> 3 \times \text{ULN}$ and International Normalized Ratio (INR) > 1.5 (If INR testing is applicable/evaluated).
- ALT or AST $> 3 \times \text{ULN}$ with the appearance of fatigue, nausea, vomiting, right upper quadrant pain or tenderness, fever, rash and/or eosinophilia ($> 5\%$).

The investigator may determine that abnormal liver function results, other than as described above, may qualify as moderate or severe abnormalities and require additional monitoring and follow-up.

Follow-up Procedures

Confirmed moderate and severe abnormalities in hepatic functions should be thoroughly characterized by obtaining appropriate expert consultations, detailed pertinent history, physical examination and laboratory tests. The site staff is to complete the liver abnormality case report form (LA-CRF). Subjects with confirmed abnormal liver function tests (LFTs) should be followed as described below.

Confirmed moderately abnormal LFTs should be repeated 2 to 3 times weekly then weekly or less if abnormalities stabilize or the study drug has been discontinued and the subject is asymptomatic.

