Severe hepatic liver function abnormalities as defined above, in the absence of another etiology, may be considered an important medical event and may be reported as a SAE. The sponsor should be contacted and informed of all subjects for whom severe hepatic liver function abnormalities possibly attributable to study drug are observed.

To further assess abnormal hepatic laboratory findings, the investigator is expected to:

- Obtain a more detailed history of symptoms and prior or concurrent diseases. Symptoms and new-onset diseases is to be recorded as “AEs” within the eCRF. Illnesses and conditions such as hypotensive events, and decompensated cardiac disease that may lead to secondary liver abnormalities should be noted. Nonalcoholic steatohepatitis is seen in obese hyperlipoproteinemic and/or diabetic subjects, and may be associated with fluctuating AT levels. The investigator should ensure that the medical history form captures any illness that predates study enrollment that may be relevant in assessing hepatic function.
- Obtain a history of concomitant drug use (including nonprescription medication, complementary and alternative medications), alcohol use, recreational drug use and special diets. Medications, is to be entered in the eCRF. Information on alcohol, other substance use and diet should be entered on the LA-CRF or an appropriate document.
- Obtain a history of exposure to environmental chemical agents.
- Based on the subject’s history, other testing may be appropriate including:
 - Acute viral hepatitis (A, B, C, D, E or other infectious agents),
 - Ultrasound or other imaging to assess biliary tract disease,
 - Other laboratory tests including INR, direct bilirubin.
- Consider gastroenterology or hepatology consultations.
- Submit results for any additional testing and possible etiology on the LA-CRF or an appropriate document.

Study Treatment Discontinuation

In the absence of an explanation for increased LFT’s, such as viral hepatitis, preexisting or acute liver disease or exposure to other agents associated with liver injury, the subject may be discontinued from study treatment. The investigator may determine that it is not in the subject’s best interest to continue study treatment. Discontinuation of study treatment should be considered if:

- ALT or AST $> 8 \times$ ULN.
- ALT or AST $> 5 \times$ ULN for more than 2 weeks.

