6.5.3 Liver Safety Assessment

The liver safety assessments will be summarized by the categories below based on the measurement from Alkaline Phosphatase (ALP), Alanine Transaminase (ALT), total bilirubin (TBIL), Aspartate Transaminase (AST), and their combination. These parameters will be based on measurements from a central laboratory.

The subjects highest value from Day 1 to Day 84 IA or Day 180 IM or EOT will be used. This criterion is without regards to the subjects baseline value.

- ALT > 3xULN, > 5xULN, > 10xULN, > 20xULN
- Total Bilirubin > 2xULN
- (ALT or AST > 3xULN) and Total Bilirubin > 2xULN
- (ALT or AST > 3xULN) and ALP < 2xULN and Total Bilirubin > 2xULN

The last 2 criteria to where 2 or more parameters are evaluated will be with the measurements on the same day or up to 1 day apart. The samples within 1 day to be considered. For example, if ALT is on day 10, ALP is on day 11 and TBIL is on day 12, this data should be considered. If ALT and ALP is on day 10, and TBIL is on day 11, this data should be considered.

The samples within 1 day apart can be used however the last criterion with 2 parameters, all 3 should be from the same day to be considered. For example, if ALT is on day 10

An eDish display plot of all patients will be created. The step-one eDISH including ALT alanine aminotransferase, TBL total bilirubin, eDISH evaluation of drug-induced serious hepatotoxicity, ULRR upper limit of reference range or normal will be created with all patients plotted.

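### The SAP 6.5.3 liver table counts AST only when bilirubin is also above 2xULN and has no 8xULN cut, so AST-led severe cases can miss every row and ALT between 8 and 10xULN cannot be read as severe

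*SAP*

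**What the plan says.** SAP 6.5.3 states that the liver categories are based on ALP, ALT, "total bilirubin (TBIL), Aspartate Transaminase (AST), and their combination". It then lists seven categories:

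- four ALT levels: "ALT > 3xULN, > 5xULN, > 10xULN, > 20xULN";
- one bilirubin level: "Total Bilirubin > 2xULN";
- two combined rows. The first is ALT or AST above 3xULN with bilirubin above 2xULN. The second adds an ALP condition and reads, after its opening bracket, "ALT or AST > 3xULN) and ALP < 2xULN and Total Bilirubin > 2xULN".

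The value classified is a peak: "The subjects highest value from Day 1 to Day 84 IA or Day 180 IM or EOT will be used". The section also plans an eDISH plot of ALT against total bilirubin.

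Protocol Appendix 12.5 treats ALT and AST alike. Its table calls an abnormality severe when ALT or AST exceeds 3xULN and bilirubin exceeds 2xULN. It then says "the subject should be considered to have severe hepatic abnormalities for any of the following" and gives four more criteria, each on ALT or AST:

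- above 8xULN;
- above 5xULN for more than 2 weeks;
- above 3xULN with INR above 1.5, if INR is evaluated;
- above 3xULN with listed symptoms or eosinophilia.

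The same levels recur under "Discontinuation of study treatment should be considered if".

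**The concern.** The liver table is where a reader will look for a count of liver signals. Protocol 1.4 singles out liver toxicity for close monitoring. In the earlier pediatric study (Protocol 1.2), one of the two withdrawals for adverse events was for raised liver enzymes considered drug-related.

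The table announces AST as a basis but does not use it unless bilirubin is also raised, and its cut-points skip the 8xULN level that the protocol uses. An AST-led case that the protocol calls severe can therefore be missing from the liver summary. An ALT-led case above 8xULN but not above 10xULN is present but looks no different from a milder one.

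**Working it through.** The plan states no figure to reproduce; the study is descriptive and has no formal sample size calculation. The check is whether each child who is severe under Appendix 12.5 reaches some SAP row.

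**Step 1. Rows.** 4 (ALT) + 1 (bilirubin) + 2 (combined) = 7. AST can place a child only in the two combined rows, and both need bilirubin >2xULN. So a child severe by AST alone, with ALT ≤3xULN and bilirubin ≤2xULN, meets no row.

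**Step 2. Example children** (values in xULN; normal INR, no symptoms, no prolonged elevation; ALP 1).

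| ALT | AST | Bilirubin | Severe under Appendix 12.5? | SAP rows met |
|---|---|---|---|---|
| 2 | 9 | 1 | Yes (>8) | None |
| 9 | 1 | 1 | Yes (>8) | ALT >3, >5 |
| 6 | 1 | 1 | No | ALT >3, >5 |
| 12 | 1 | 1 | Yes (>8) | ALT >3, >5, >10 |
| 2 | 9 | 2.5 | Yes (both the >8 and the combined criterion) | Bilirubin >2; both combined rows |

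The second and third children cannot be told apart. The number with ALT >8xULN is known only to lie between the >10 count and the >5 count.

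**Step 3. Coverage over a grid of assumed values.** ALT and AST each took 1, 2, 3.5, 6, 9, 12 or 25; bilirubin 1 or 2.5; ALP 1 or 2.5; INR 1 or 1.6; symptoms yes/no; prolonged elevation yes/no. That gives 7 × 7 × 2⁵ = 1568 profiles.

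- Pairs with ALT or AST >3: 49 − 4 = 45.
- With bilirubin 2.5, all are severe: 45 × 2 × 8 = 720.
- With bilirubin 1, there are also 720, of which 34 are not severe. These have normal INR and no symptoms, and a peak of 3.5 (5 pairs × 2 duration states) or 6 without prolonged elevation (7 pairs), times 2 ALP values: (10 + 7) × 2 = 34. That leaves 686.
- Protocol-severe profiles: 720 + 686 = 1406.
- In no SAP row: ALT 1 or 2, AST >3, bilirubin 1, which is 2 × 5 × 2 × 8 = 160, less 2 × 2 × 3 = 12 not severe, so **148**.

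All 148 are AST-led with ALT ≤3xULN and bilirubin ≤2xULN. They arise under all four additional criteria and never under the combined one. No ALT-led severe profile misses every row. These counts show logical coverage; they are not incidences.

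**Step 4. After adding ALT-or-AST rows at >3, >5, >8, >10 and >20xULN.** Profiles in no row fall from 148 to 0. AST 9xULN appears at >3, >5 and >8, and ALT 9xULN separates from ALT 6xULN. The duration, INR and symptom criteria still cannot be identified from a table of peaks.

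**Step 5. Do other outputs supply the count?** SAP 6.5.2 classes each result as low, normal or high, so AST at 1.1xULN and at 20xULN are both high. It names days 7, 28, 56 and 84 or EOT for by-visit reporting. Protocol Table 1 schedules hepatic panels on days 3 and 7 and then weekly to day 84: 13 panels, of which 4 fall on named days and 9 do not. An AST peak on day 14 or 21 can miss that summary. Listings hold the values but give no count, and eDISH plots the AST 9xULN child at ALT 2, bilirubin 1.

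**The case against.** A reader might infer that any child with a protocol-severe abnormality can vanish from the liver table, or that the trial cannot say how many met its own definition. The documents do not support either.

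- The main severe definition, with bilirubin above 2xULN, is an SAP row, AST included.
- ALT-led severe cases always reach at least one row.
- AST remains in the hepatic panel statistics, shift tables and subject listings. Appendix 12.5 requires a liver abnormality case report form for confirmed moderate and severe cases. With about 30 children, cases above 8xULN can be found by reading listings.

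It is also fair to say that nothing obliges the SAP to tabulate Appendix 12.5, which governs monitoring of individual children. Protocol 7.5.2 promises only descriptive statistics, shifts and listings, and the liver categories go beyond that. No efficacy result or planned decision depends on this table.

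All of that stands and limits the point. It does not remove it: SAP 6.5.3 itself names AST as a basis and then does not use it at any level without raised bilirubin. Adverse event tables are not a dependable substitute either. Protocol 5.5.1.1 lets clinically significant abnormalities linked to the underlying disease go unreported unless more severe than expected, and Appendix 12.5 says severe cases may be reported as serious, although Protocol 5.5.1.2 is stricter.

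**Conclusion.** The point holds as a gap in the dedicated liver summary, not in the data. Two consequences are certain from the text: an AST-led severe case with ALT ≤3xULN and bilirubin ≤2xULN is in no row, and ALT above 8 but not above 10xULN shows only as above 5xULN. The four additional severe criteria have no count of their own.

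How often this will happen cannot be estimated, because the documents give no rate for AST-led elevation. For scale only, one uncounted child in an assumed 30 is 1/30 = 3.3% (exact 95% CI 0.1 to 17.2%) reported as 0/30 (0 to 11.6%); that arithmetic applies to any single event in this trial. The conclusion assumes the seven listed categories are the complete table. It is worth correcting because the change is cheap, but it does not threaten the study's conclusions.

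**What to change.** 1. Replace the ALT-only row with three sets, ALT, AST, and ALT or AST, each at >3, >5, >8, >10 and >20xULN, using the highest on-treatment value as now. Keep the bilirubin and combined rows.
2. Add one count of children meeting any Appendix 12.5 severe criterion, with these derivations written into the SAP:
   - whether confirmation is required, since Appendix 12.5 grades confirmed abnormalities and asks for retesting within 72 hours;
   - duration as >5xULN on consecutive samples spanning more than 2 weeks (three samples exactly a week apart span 14 days, which is not more than 2 weeks);
   - INR, where evaluated, within a stated window of the transaminase value;
   - symptoms from adverse events within a stated window, and eosinophils from hematology.

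The source data are already collected, and no clinical rule changes. The cost is SAP and table-shell text plus a little extra programming. INR is scheduled through day 84 only at screening and days 7, 28, 56 and 84 or EOT, and panels for IM subjects after day 84 are monthly, so the INR and duration criteria will be under-ascertained there unless unscheduled samples are taken. A footnote should say so.

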6.5.4 Vital Signs

Descriptive statistics will be used to summarize vital sign results and changes from baseline for subjects in the SAF by treatment day from day 1 to day 84 (or EOT).

Vital signs data will be displayed in listings.

The baseline visit (screening predose period day -5 to 5) is the last non-missing measurement value taken prior to initial study drug administration. Post baseline visits will include vital signs measured prior to and again approximately 1 hour after the end of each infusion.

Vital signs (systolic blood pressure, diastolic blood pressure, pulse rate, respiratory rate and temperature) will be summarized using mean, standard deviation, minimum, maximum and median by Treatment Visit. Within subject change in vital sign values between visits will be summarized from baseline on.

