1.2 Nonclinical and Clinical Data

An overview of the nonclinical and adult clinical data of isavuconazole can be found in the latest version of the investigator's brochure (IB).

Isavuconazole has been investigated in a phase 1 pharmacokinetic, safety and tolerability study in pediatric subjects following intravenous administration. In this study, a total of 27 pediatric subjects received at least 1 dose of study drug (Protocol 9766-CL-0046). Nine subjects were between 1 and < 6 years of age, 8 subjects were between 6 and < 12 years of age and 10 subjects were between 12 and < 18 years of age. A majority of subjects were white and male. Most subjects had an underlying malignancy. Subjects weighing \leq 40 kg received 10 mg/kg of isavuconazonium sulfate, and subjects > 40 kg received 372 of isavuconazonium sulfate intravenously daily, after a loading regimen.

The vast majority of subjects experienced at least 1 adverse event (AE), and serious adverse events (SAEs) were experienced by about half of all subjects, which is expected given the medical history of the subjects enrolled. About a third of subjects experienced drug-related AEs. Important drug-related events included gastrointestinal (GI) disorders and infusion-related reactions. Two subjects were withdrawn from the study due to an AE. The events leading to withdrawal were increased liver enzymes and QT prolongation, and both events were considered related to study drug. No differences were observed in the AE experience between the 3 age cohorts.

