5.4 Safety Assessment

5.4.1 Vital Signs

Vital signs (temperature, pulse rate and blood pressure) are to be measured within 1 hour before the start and approximately 1 hour after the end of each infusion on dosing days. No additional vital signs are needed on dosing days for oral administration. Temperature to be taken as per institution's policy based on age of subject. Vital signs will be collected as shown in the schedule of assessments [Table 1 and Table 2]. When vital signs are scheduled for the same time as a blood sample, the vital signs will be taken before the blood sample.

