6 DISCONTINUATION

6.1 Discontinuation of Individual Subject(s) From Study Treatment

A discontinuation from treatment is a subject who enrolled in the study and for whom study treatment is permanently discontinued for any reason. The reason for discontinuation from study treatment must be documented in the subject's medical records.

A subject must discontinue study treatment for any of the following reasons:

- Subject requests to stop treatment.
- Any clinical AE, laboratory abnormality or intercurrent illness, in the opinion of the investigator, indicates continued treatment is not in the best interest of the subject.
- Parent(s) or legal guardian withdraws consent.
- Subject experiences a systemic infusion-related reaction (IRR) such as hypotension, dyspnea, chills, dizziness, paresthesia and hypoesthesia attributable to study drug during or shortly after the intravenous administration; however, in case of an infusion-related reaction, the infusion must be stopped immediately and the subject must be discontinued from treatment.

Note: If the IRR signs and symptoms are mild and self-limiting, the subject may continue in the study at the discretion of the investigator.

- Serious hypersensitivity or severe skin reactions, such as anaphylaxis or Stevens Johnson syndrome, have been reported during treatment with other azoles. If subject develops a severe hypersensitivity adverse reaction without alternative etiology, the subject must be discontinued from treatment.
- Investigator's decision that further treatment is not in the best interest of the subject.
- Female subject becomes pregnant.
- Subject is lost to follow-up despite diligent efforts to contact.

Discontinuation of the subject from treatment should be considered if a subject experiences an increase in liver enzymes. For specific liver abnormalities, refer to [Appendix 12.5].

All subjects who discontinue study treatment will remain in the study and should continue to be followed for protocol specific follow-up procedures as outlined in [Table 1 Schedule of Assessments]. The only exception to this is when the subject specifically withdraws consent for any further contact, with him/her or persons previously authorized by the participant to provide this information.

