7.5.3 Vital Signs

Descriptive statistics will be used to summarize vital sign results and changes from baseline for subjects in the SAF by treatment visit.

Vital signs data will be displayed in listings.

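### Vital signs are read before and after each infusion, but the SAP's same-day averaging rule merges the two readings and no paired post- minus pre-infusion change is planned

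*SAP*

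**What the plan says.** **Measurement.** Protocol 5.4.1 has temperature, pulse and blood pressure "measured within 1 hour before the start and approximately 1 hour after the end of each infusion on dosing days". Children dosed by mouth need no extra readings on dosing days.

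**Summary.** SAP 6.5.4 takes both readings in: "Post baseline visits will include vital signs measured prior to and again approximately 1 hour after the end of each infusion". For systolic pressure and "diastolic blood pressure, pulse rate, respiratory rate and temperature) will be summarized using mean, standard deviation, minimum, maximum and median by Treatment Visit", these are the only statistics named. Baseline is the last available value before the first dose. The planned change is stated as "Within subject change in vital sign values between visits will be summarized from baseline on". Protocol 7.5.3 is the same in substance: "Descriptive statistics will be used to summarize vital sign results and changes from baseline for subjects in the SAF by treatment visit". Individual values are listed. SAP 6.5.8 repeats vital signs by age group and infection type, and SAP 6.5.7 adds nothing.

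**Handling rules.** SAP 6.9 names vital signs among the data summarised by analysis window. Its table goes from baseline, which ends at the first dose, straight to Day 2. The last paragraph of SAP 6.9.1 says how to choose among several observations in a window. Where several fall on the same day, continuous values are averaged. No exception is made for readings that bracket an infusion.

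**Clinical background.** Of the earlier pediatric IV study, protocol 1.2 says: "Important drug-related events included gastrointestinal (GI) disorders and infusion-related reactions". The discontinuation criteria in protocol 6.1 include: "Subject experiences a systemic infusion-related reaction (IRR) such as hypotension, dyspnea, chills, dizziness, paresthesia and hypoesthesia attributable to study drug".

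**The concern.** Readings on either side of an infusion are useful because of the difference between them. The rationale for protocol Amendment 3 says as much: the extra vital signs serve the monitoring of intravenous dosing. The SAP collects the pair, defines no analysis of it, and has a general rule that merges it.

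Two things are lost. Averaging shrinks any acute fall before it reaches the table. Measuring change from a value taken before the first dose mixes the effect of the infusion with whatever has happened to the child's blood pressure since then.

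Safety is a study objective and vital signs are a named safety endpoint. The SAP gives the other measured safety endpoints some categorical summary: shift tables for laboratory tests (6.5.2), threshold categories for liver tests (6.5.3), and counts of children who worsened for ECGs (6.5.5). Vital signs have none, so the averaged by-visit statistics are the whole tabulated result.

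**Working it through.** The plan gives no figure on this point, so there is none to reproduce. The check applies the SAP's own rules to simple cases. Blood pressure values and the number of IV-treated children are assumed.

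**1. Size of the averaging effect.** Inputs: two readings per infusion (protocol 5.4.1); one infusion on a maintenance day; three on a loading day (every 8 hours, six doses over Days 1 and 2, protocol 5.1.1); same-day values averaged (SAP 6.9.1). Let one post-infusion reading differ by d from the others that day, all others being at baseline. With k infusions the day has 2k readings and the tabulated change is d/(2k). For d = -30 mmHg:
- k = 1: -30/2 = -15
- k = 3: -30/6 = -5

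If all three loading infusions produced the fall, the average would be 3 × (-30)/6 = -15. On Day 1 the reading before the first infusion is itself the baseline. If it is left out of the average, five readings remain and an isolated fall shows as -30/5 = -6.

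**2. What a visit table would show.** Assume 15 IV-treated children at a maintenance visit, one falling 30 mmHg and fourteen unchanged.
- Paired post- minus pre-infusion change: mean -30/15 = -2.0, SD 30/√15 = 7.7, minimum -30.
- Under the SAP rule: mean -15/15 = -1.0, SD 15/√15 = 3.9, minimum -15.

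Mean, SD and minimum are all halved.

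**3. Drift from baseline.** Assume one child with 85 mmHg before the first dose, 100 before a later infusion and 80 after it.
- Paired change: 80 - 100 = -20
- Post-infusion value against baseline: 80 - 85 = -5
- Same-day average against baseline: (100 + 80)/2 - 85 = +5

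A 20 mmHg fall across the infusion is tabulated as a 5 mmHg rise.

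**4. Day 1.** SAP 6.5.4 summarises from Day 1, and Appendix 1 has a Day 1 visit. The SAP 6.9 table, which is the one said to govern vital signs, has no window after the first dose on Day 1. Where the readings after the first loading infusions would appear is unclear.

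**5. Time between the readings.** Up to 1 hour before the start, plus about 1 hour of infusion, plus about 1 hour after the end, gives roughly 2 to 3 hours.

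**6. How a threshold count would behave.** Infusions on scheduled days are 3 + 3 + 3 = 9 to Day 14 and 3 + 3 + 13 = 19 to Day 84 (protocol Table 1). Assume the percent change in systolic pressure across an infusion is normal with mean 0 (no drug effect), SD 8 to 12%, and independent between infusions. The chance of a fall of at least 20% is Φ(-20/SD), which is 0.6 to 4.8% per infusion. The chance that a child has at least one is 1 - (1 - p)^n, which is 5.5 to 35.6% for n = 9 and 11.2 to 60.6% for n = 19.

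**The case against.** **Falls that matter are already counted.** A clinically significant abnormal vital sign is reported as an adverse event unless it is explained by the underlying disease and no worse than expected (protocol 5.5.1.1). SAP 6.5.1 tabulates treatment-emergent events by severity, relationship, age cohort and time interval. A systemic infusion reaction that is more than mild leads to discontinuation (protocol 6.1), and a DSMB reviews safety throughout. This stands. A reader might infer that hypotension after infusion would go uncounted in this trial, but the documents do not support that. What escapes the tables is measured falls judged not significant, or as expected from the underlying disease. Adverse event counts do not, however, repair a vital-sign table built on averaged readings.

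**Both readings may yet be shown separately.** SAP 6.5.4 names both, and SAP 6.1 leaves table formats to TLF specifications that are not among the documents. This also stands in part: it is not certain that the programmed tables will average the pair. But separate rows would yield only a mean difference by subtraction, without its spread, and the SAP text as it stands points to averaging.

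**The first infusion has a paired change.** Its pre-infusion value is the baseline, so change from baseline to the first post-infusion reading is the paired change. That is right, provided the reading is not averaged with later ones and has a Day 1 row to go in. Neither is secured.

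**The pair is an imperfect detector.** With readings 2 to 3 hours apart, a brief fall during the infusion can be over before the second one. This limits what a paired table can show, and the table should say so.

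**A count of falls would be hard to interpret.** A reader might infer that the SAP must report how many children had a fall of some fixed size, with an exact confidence interval. The documents set no such threshold. On the assumptions in step 6, a 20% limit could flag up to about 61% of children by Day 84 with no drug effect, and there is no control arm to set against that.

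**Conclusion.** The point holds as a defect in how a named safety endpoint is tabulated. Under the SAP's written rules, an isolated post-infusion fall is halved on a day with one infusion (-30 becomes -15) and cut to a sixth on a day with three (-5). In the assumed 15-child example the visit table shows mean -1.0, SD 3.9 and minimum -15. No paired change is defined, and Day 1 after the first dose has no window in SAP 6.9.

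The sizes rest on assumed blood pressures, on the other readings that day being at baseline, and on the averaging rule being applied as written. The absence of a paired analysis and of an exemption from averaging rests on the text alone. The defect does not threaten the trial: analyses are descriptive, individual values are listed, and clinically significant falls reach the adverse event tables. It is worth correcting because the data are already collected for this purpose.

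**What to change.** Before database lock, amend SAP 6.5.4, 6.9 and 6.9.1:

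1. Exempt infusion-day vital signs from the same-day averaging rule.
2. Keep pre- and post-infusion readings as separate time points, including each Day 1 and Day 2 loading infusion that has both, and add a post-dose Day 1 window to the 6.9 table.
3. For IV-treated children, summarise the paired post- minus pre-infusion change in systolic pressure, diastolic pressure and pulse, overall and by the age groups in SAP 6.5.8.
4. State in the table notes that the readings are about 2 to 3 hours apart and can miss a brief fall.

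Optionally, add the number of children and of infusions with a fall beyond a limit fixed in advance. Present it as description, beside the treatment-emergent adverse events, and do not attribute it to drug.

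The cost is SAP wording and one added table. No protocol amendment and no new measurement are needed.
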